4 LIST OF ABBREVIATIONS

Term	Definition
AAV	Adeno-Associated Virus
ACEI	Angiotensin-converting enzyme inhibitors
AE	Adverse Event/Experience
AICD	Automatic implantable cardioverter-defibrillator
ARB	Angiotensin receptor blocker
ARNI	Angiotensin receptor/neprilysin inhibitor
ASA	Acetylsalicylic acid
ASO	Antisense oligonucleotide
AUC	Area Under the Curve
BB	Beta blocker
C	Celsius
CBC	Complete blood count
CFR	Code of Federal Regulations
CI	Contractility index
CK	Creatine kinase
cm	Centimeter
C _{max}	Maximum Plasma Concentration
CMP	Comprehensive metabolic panel
CMR	Cardiac Magnetic Resonance
COX	Cyclooxygenase
CPK	Creatine Phosphokinase
CRF	Case Report Form
CPI	Cumberland Pharmaceuticals Inc.
DKO	Double Knockout
DMD	Duchenne Muscular Dystrophy
dSG KO	Delta-sarcoglycan knockout
E/A	early (E) to late (A) ventricular filling velocities
ECHO	echocardiography
eCRF	Electronic case report form
EF	Ejection fraction
F	Fahrenheit
FDA	Food and Drug Administration
FEV1	Forced Expiratory Volume in 1 Second
FS	Fractional shortening

Term	Definition
FVC	Forced vital capacity
GCP	Good Clinical Practice
GI	Gastrointestinal
ICH	International Conference on Harmonization
IEC	Independent Ethics Committee
ife	Ifetroban
IMP	Investigational Medicinal Product; synonymous with “study drug”
INR	International normalized ratio
IRB	Institutional Review Board
ITT	Intent-To-Treat
kg	Kilogram
KO	Knockout
L	Liter
LGE	Late gadolinium enhancement
LGMD	Limb-Girdle Muscular Dystrophy
LVEF	Left ventricle ejection fraction
MedDRA	Medical Dictionary for Regulatory Activities
MEP	Maximum expiratory pressure
mg	Milligram
MIP	Maximum inspiratory pressure
mL	Milliliter
MRI	Magnetic Resonance Imaging
ng	Nanogram
NHS	Natural history study
NMM	Neuromuscular Module
Non-MR	Non-magnetic resonance
PAB	Pulmonary arterial banding
PAH	Pulmonary arterial hypertension
PedsQL	Pediatric Quality of Life Inventory
PEF	Peak expiratory flow
PFT	Pulmonary Function Test
PK	Pharmacokinetic
PT	Prothrombin time
PTT	Partial thromboplastin time
QMT	Quantitative Muscle Testing

Term	Definition
RV	Right ventricle
SAE	Serious Adverse Event/Experience
SGLT2	Sodium glucose cotransporter-2
SOC	System Organ Class
t _{1/2}	Half-life
TEAE	Treatment Emergent Adverse Event
T _{max}	Time of maximum plasma concentration
TPr	Thromboxane Prostanoid Receptor
TXA2	Thromboxane A2
TXAS	Thromboxane A2 Synthase
Ves	End systolic volume
yo	years old

5 INTRODUCTION

This study is to be performed in accordance with the International Conference on Harmonization's (ICH) E6 guideline for Good Clinical Practice (GCP), the ethical principles that have their origin in the Declaration of Helsinki, and Title 21 of the Code of Federal Regulations (CFR) Parts 50, 56 and 312.

5.1 Background Information

5.1.1 Duchenne Muscular Dystrophy

Duchenne muscular dystrophy (DMD) affects approximately one of every 3,300 male births worldwide ([Quinlivan 2009](#)) and is caused by the complete absence of the sarcolemmal protein dystrophin as a result of anomalies in the X-linked DMD gene. Loss of dystrophin leads to inexorable damage to skeletal and cardiac muscle, with cardiomyopathy increasingly recognized as a major cause of death ([Romfh 2010](#)). Due to ongoing muscle damage, patients with DMD have markedly elevated serum levels of the muscle protein creatine kinase (CK), which may be 10× to over 100× the normal limit, and an elevated CK level is a diagnostic sign ([Konagaya 1986](#)). There is currently no cure for DMD. Current treatment is limited to the management of symptoms which is fueling investigations aimed at targeting the genetic defect. Several therapies are in various stages of development, including utrophin up-regulation, stop codon read-through therapy, viral gene therapy, cell-based therapy and exon skipping. These have mainly focused on improving skeletal muscle function without addressing the cardiac aspects of the disease, which may aggravate cardiomyopathy. For this reason, preclinical and clinical focus on improving heart function is essential.

The absence of dystrophin in the heart renders cardiomyocytes more sensitive to stretch-induced damage. This results in increased levels of intracellular calcium, thereby activating calpains and proteases that consequently degrade contractile proteins, promoting cellular death and fibrosis, all contributing to the development of cardiomyopathy ([D'Amario 2017](#); [van Westering 2015](#)). Animal and human data demonstrate the myocardial damage is evident before functional decline such as a reduction in left ventricular ejection fraction (LVEF) ([Rafael-Fortney 2016](#)), endorsing a strategic treatment window for initiating cardioprotective treatment at earlier stages of myocardial disease while EF is preserved. LV systolic strain measured by cardiac magnetic resonance imaging (CMR) is a more sensitive measure of cardiac function, has high reproducibility ([Soslow 2016](#)) – a critical feature when testing hypotheses in patients with rare diseases to support efficient sample size reductions – and is abnormal in even the youngest boys with DMD well before EF drops ([Hor 2009](#)). Eplerenone was recently shown using CMR to attenuate the decline

of cardiac function compared to placebo ([Raman 2015](#)). The benefit was greater at an early stage of cardiac involvement.

5.1.2 Ifetroban

[figure not shown]
Ifetroban is a new chemical entity under development by Cumberland Pharmaceuticals Inc. (CPI) for Duchenne Muscular Dystrophy (DMD) and other diseases. The current formulation of oral ifetroban is a 50 mg capsule. Ifetroban is a well characterized pharmacological antagonist of the thromboxane prostanoid receptor (TPr), and has been studied previously in healthy volunteers and subjects with cardiovascular diseases. CPI studied the safety of the intravenous formulation of ifetroban in subjects with hepatorenal syndrome and portal hypertension. The oral formulation of ifetroban is under phase 2 investigation in patients with aspirin exacerbated respiratory disease, portal hypertension and systemic sclerosis. A large safety database exists from this work in addition to the many ifetroban clinical studies conducted by Bristol-Myers Squibb.

Thromboxane A2 (TXA2) is a member of the prostanoid family of arachidonic acid metabolites generated by the sequential action of three enzymes – phospholipase A2, cyclooxygenase (COX)-1 or COX-2 and TXA2 synthase (TXAS). TXA2 directs multiple biological processes via its cell surface receptor, the TPr. The biosynthesis of TXA2 as well as isoprostanes, nonenzymatic free radical-derived products of arachidonic acid that can activate the TPr in vivo ([Audoly 2000](#)), is elevated in numerous cardiovascular and inflammatory diseases, as is expression of the receptor itself ([Katugampola 2001](#)). TXA2 has been widely implicated in a range of cardiovascular diseases, owing to its acute and chronic effects in promoting platelet aggregation, vasoconstriction, and proliferation ([Smyth 2010](#)).

The G protein-coupled TPr, expressed in platelets, immune cells, smooth muscle, and cardiomyocytes, has deleterious consequences of activation in the heart that mirrors the fibrosis and calcium alterations associated with MD cardiomyopathy. TPr activation contributes to LV hypertrophy and heart failure in mouse models of systemic hypertension and Gh-overexpression ([Francois 2004; Francois 2008; Zhang 2003](#)). The best-characterized signaling pathway of the TPr is via Gq ([Huang 2004; Kinsella 1997](#)), and results in phospholipase C activation, calcium mobilization via intracellular stores, and protein kinase C activation. In ventricular cardiomyocytes, TPr activation causes increased intracellular calcium, arrhythmia, and cell death in ventricular cardiomyocytes ([Wacker 2009](#)), and administration of a TPr agonist induces ventricular arrhythmias in rabbits ([Wacker 2006](#)). Activation of the TPr is pro-fibrotic in multiple systems ([Acquaviva 2013; Comporti 2008; Gelosa 2011](#)), and we have recently shown that TPr antagonism dramatically decreases right ventricular fibrosis and improves cardiac function in a pressure-overload model of pulmonary arterial hypertension ([West 2016](#)). These studies also

demonstrated the cardioprotective effects of ifetroban were not duplicated by inhibiting cyclooxygenases with aspirin or by blocking TXA2 production with a thromboxane synthase inhibitor, ozagrel (Figure 5-1). These findings suggest TPr blockade by ifetroban may have a durable benefit on preserving cardiac function in subjects with DMD. Furthermore, available TPr is likely to be activated during DMD. Isoprostanes formed during oxidative stress and known to cause fibrosis through the receptor (Acquaviva 2013; Comporti 2008), is increased in both BMD and DMD patients (Grotto 2008), as well as in heart failure patients (Cracowski 2000). Thus, although the role of the TPr in DMD has not previously been studied, the ligand availability and known signaling actions position the receptor to impact cardiomyopathy and the decline of cardiac function in DMD, where it may be an important therapeutic target.

Figure 5-1 Ifetroban decreases RV fibrosis and improves cardiac function

[figure not shown]

Antagonism of the TPr with ifetroban, but not inhibition of cyclooxygenase (aspirin; ASA) or thromboxane synthase (ozagrel; oza), decreases RV fibrosis 2 weeks after pulmonary arterial banding (PAB; A-B). Ifetroban treatment also improved RV contractility index (CI) and normalized stiffness (Tau) and end systolic volume (Ves) at 3 weeks post-PAB (C; n=7-14), and prevented the decrease in fractional shortening at 6 weeks post-PAB (D). *, p<0.05, **, p<0.01 by one-way ANOVA/Sidak's posttest. Source: [West 2016](#)

Recently, the effects of long-term antagonism of the TPr on the development of fibrosis and cardiomyopathy associated with muscular dystrophy were investigated. Treatment with ifetroban increased animal survival and improved the cardiac phenotype in three different murine models of MD (Figure 5-2): the δ -sarcoglycan knockout (dSG KO) mouse model of Limb-Girdle Muscular Dystrophy (LGMD); utrophin/dystrophin double knockout (DKO) mice and mdx/mTR mice, two models of severe DMD. TPr antagonism improved cardiac output in two models of severe DMD, and increased ejection fraction while decreasing cardiac fibrosis, TGF β signaling, and expression

of matricellular genes in LGMD mice. In dSG KO LGMD mice, the normalized ejection fraction reflected improved diastolic filling, via decreased fibrosis and corrected calcium decay and cardiomyocyte relaxation, compared with vehicle-treated mice. Ifetroban helped to increase expression of claudin-5 and nNOS protein, which have also been shown to improve cardiac function in DMD (Lai 2014), and normalized expression of select genes typically upregulated in DMD (West 2018). Altogether, these results suggest that the TPr is activated in DMD and contributes to the cardiac phenotype. The inhibition of LV fibrosis and dysfunction by ifetroban is encouraging as LV dilation and the development of depressed LVEF are common findings in subjects with DMD and often present in the second decade of life. DMD subjects assessed using late gadolinium enhancement (LGE) by CMR demonstrated progressive myocardial fibrosis in the LV that was found to increase with age and correlate with a decline in LVEF (Tandon 2015). This preclinical evidence provides the medical rationale in this current study, which aims to test the hypothesis oral ifetroban may have a cardioprotective effect in DMD.

Figure 5-2 Ifetroban reduces LV fibrosis, improves cardiac function & survival in DMD

Treatment with the TPr antagonist ifetroban (ife) improves survival (A), normalizes fractional shortening (FS) and ejection fraction (B) and decreases epicardial interstitial fibrosis (C; n=4-5) in dSG KO LGMD male mice. Fibrotic area was quantified from trichrome-stained slices in Leica Image Analysis using the same trichrome-defined image mask for all slides. Ifetroban also decreased phospho-SMAD2/3, a TGF β signaling molecule (E; n=2). Comparisons by unpaired t-tests shown; intervening lanes were removed from blot in E. Utrophin-dystrophin double knockout DMD mice (DKO) and dystrophin KO mice with short telomeres (G2 mdx/mTR) have increased survival (E, G) and improved LV cardiac index with ifetroban treatment (F, H). The results of log-rank test (E, G) or unpaired t-test (F, H) comparisons are shown. (H) is male mice only, due to sex differences of cardiac output in fully grown mice.*. $p < 0.05$ by log-rank test. dSG KO=delta-sarcoglycan knockout.

Source: West 2019

5.2 Stage of Development

CPI-IFE-007 is randomized, double-blind, placebo-controlled, multiple dose study with an open-label extension to determine the safety, pharmacokinetics and efficacy of two dose ranges of oral ifetroban in subjects with DMD.

Approximately 48 subjects will be randomly assigned to one of three treatment groups for 12 months of treatment: low-dose ifetroban, high-dose ifetroban or matching placebo, with 24 subjects within each disease stage, early (LVEF > 45%) or advance (current/historical LVEF 35%-45%). Patients who complete 12 months of treatment are eligible to participate in a repeatable open-label extension period of 12 months.

5.3 Trial Rationale

The current trial is based on preliminary data which evaluated ifetroban using preclinical models of PAH and DMD to prevent cardiac fibrosis and dysfunction. Blockade of the TPr with ifetroban dramatically decreased right ventricular fibrosis and improved cardiac function in a pressure-overload model of PAH (West 2016; [Figure 5-1](#)). Aside from the right ventricle, TPr antagonism with ifetroban decreased LV cardiac fibrosis and improved cardiac function and survival in animal models of LGMD and DMD ([Figure 5-2](#)). Ifetroban also normalized plasma levels of troponin I, a biomarker for cardiac injury, and decreased cardiac expression of the atrial and brain natriuretic peptides, clinical biomarkers of cardiac dysfunction (not shown). These results provide the medical rationale to study ifetroban as a potential novel treatment for DMD. CPI-IFE-007 is a safety study designed to investigate the pharmacokinetics and efficacy of two oral dose ranges of ifetroban compared to placebo, to treat cardiac dysfunction in DMD subjects. The current study design will leverage data from an FDA-funded DMD CM natural history study with identical CMR protocol, endpoints and procedures to supplement our analysis. This strategy will enhance statistical power and strengthen our comparator arm through the inclusion of additional matched control subjects.

5.4 Dose Rationale

Oral ifetroban doses \geq 100 mg have been shown to inhibit TPr induced platelet aggregation, with corresponding plasma C_{max} levels of > 500 ng/mL. The bioavailability of oral ifetroban capsules has previously been found to be $\approx 42\%$. Our multi-dose safety studies have found oral ifetroban at up to 500 mg daily to be safe and well tolerated however these studies did not include children. For this reason, this study aims to compare two dose ranges of oral ifetroban (a low dose and high dose based on weight) to placebo for at least twelve months. A placebo treatment arm is included to help provide data on the natural history of the disease.

5.5 Risk-Benefit Assessment

Ifetroban prevents TPr ligand binding and activation which plays a role in oxidative stress, isoprostanate generation, smooth muscle contraction and inflammation. Ifetroban has been studied in over 26 clinical studies and evaluated for safety in over 1,400 subjects. Most of these studies were conducted in subjects with cardiovascular disease. A large safety database from this work has shown no safety concerns with the use of ifetroban at doses as high as 500 mg daily. Based upon the current available data for ifetroban and the review of the data by an independent data monitoring committee, no important identified risks have been established. There is a potential risk based on the mechanism of action that treatment with a TPr antagonist may inhibit platelet function and thereby increase the risk of bleeding however multi-dose safety studies have not demonstrated an increased risk of bleeding with ifetroban. Although our clinical studies have not demonstrated abnormal laboratory findings or bleeding events as a safety concern, clinical laboratory results will be closely monitored for possible abnormalities related to clotting or bleeding in all study subjects.

Given the preclinical data, there is a potential survival benefit to study subjects treated with ifetroban. If TPr antagonism does indeed provide cardiac symptom control and improve the cardiac function for subjects with DMD, it would support the use of ifetroban as a therapeutic agent. As such, the potential risk to subjects seems reasonable compared to the potential benefit.

6 STUDY OBJECTIVES & ENDPOINTS

6.1 Primary Objective

Assess the safety of oral ifetroban in male subjects with Duchenne Muscular Dystrophy (DMD).

6.2 Secondary Objectives

Evaluate the pharmacokinetics and efficacy of oral ifetroban in DMD subjects.

6.3 Exploratory Objectives

Evaluate novel biomarkers for diagnosis and monitoring of cardiomyopathy in DMD.

6.4 Primary Endpoint

Safety and tolerability (baseline to 12 months): percentage of subjects with one or more treatment emergent adverse events (TEAE) .

6.5 Secondary Endpoints

- Pharmacokinetics (PK) – Peak plasma concentration of ifetroban after administration and its acyl glucuronide metabolite (C_{max}). Time of C_{max} (T_{max}), AUC, Clearance and

Elimination half-life (t_{1/2}). Blood samples will be collected pre-dose for all subjects and at 30, 60 (±5) minutes; and 4, 8 and 24 hours (all ± 30 minutes) post dose on Day 0 (first dose) and pre-dose and 30 minutes post-dose at Day 7 (steady-state).

- Efficacy of ifetroban over 12 months of dosing
 - Change from baseline in LVEF using CMR;
 - Change from baseline in myocardial strain using CMR;
 - Change from baseline in Pulmonary function test results including peak expiratory flow (PEF), forced vital capacity (FVC), forced expiratory volume in 1 second (FEV1), maximum inspiratory pressure (MIP), and maximum expiratory pressure (MEP);
 - Change from baseline in Pediatric Quality of Life Inventory (PedsQL) results, including the gastrointestinal (GI) module and neuromuscular module (NMM).
- Efficacy of ifetroban over 24 to 36 months of dosing (for the open label population)
 - Change from baseline or Month 12 in LVEF using CMR;
 - Change from baseline or Month 12 in myocardial strain using CMR;
 - Change from baseline or Month 12 in Pulmonary function test results including peak expiratory flow (PEF), forced vital capacity (FVC), forced expiratory volume in 1 second (FEV1), maximum inspiratory pressure (MIP), and maximum expiratory pressure (MEP);

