7 STUDY DESCRIPTION

7.1 Study Design

CPI-IFE-007 is double-blind, placebo-controlled, multicenter, dose-ranging study with an open-label extension to determine the safety, pharmacokinetics and efficacy of two dose ranges of oral ifetroban in subjects with DMD. DMD patients who meet the inclusion criteria and none of the exclusion criteria will receive oral Investigational Medicinal Product (IMP) once daily for 12 months. Subjects will be randomly assigned to one of three treatment groups, low-dose ifetroban, high-dose ifetroban or placebo, and dosed based on weight. Each treatment group will be evaluated by eight subjects with early stage (LVEF > 45%) and eight subjects with advance stage (historical/current LVEF 35% - 45%) DMD for at least six months and a maximum of 12 months. Subjects who complete 12 months of treatment will be eligible to participate in repeatable open-label extension periods of 12 months. An additional comparator group will be utilized from DMD patients evaluated in an FDA-funded natural history study (NHS) over multiple years matched to CPI-IFE-007 subjects by baseline LVEF, age, and background DMD therapy ([Soslow 2023](#)). The CPI-IFE-007 study is designed to mirror the FDA-funded DMD NHS in terms of procedures, imaging protocol, and endpoint assessments to enable valid comparisons between study populations. This design feature will facilitate the planned supplementation of the placebo arm with matched historical controls. All subjects who receive IMP will be assessed for safety. All subjects with at least one efficacy assessment post-baseline will be evaluated for efficacy. Blood and urine will be collected for standard and novel cardiac biomarkers.

The double-blind study will be conducted with two periods: a screening period of up to 12 weeks and a treatment period of up to 12 months. The open label study consisting of high-dose ifetroban treatment will be conducted in repeatable periods of 12 months.

Figure 7-1 Study Design

CBC = complete blood count; CMP = comprehensive metabolic panel; Coags = coagulation factors; ECG=electrocardiogram, Echo= echocardiography; QMT= quantitative muscle testing; PFT= pulmonary function test; QoL = quality of life; LVEF = left ventricle ejection fraction; CMR=cardiac MRI; PE = physical exam with vitals; PK=pharmacokinetics; W= week, M=month

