8.1.3 Optional Open-Label Extension

Patients who complete 12 months of treatment are eligible to participate in a repeatable open-label extension period of 12 months. Should a subject elect to participate in the open-label extension, the transition from IMP to the open-label extension should be continuous. Patients who elect to participate in the open-label extension will complete the following additional procedures.

Month 15, 18 & 21 Phone Calls

- Inquire about AEs/Serious Adverse Events (SAEs) and IMP tolerability
- Record all medication use with start date and dose; check for prohibited medications
- Confirm compliance (subject diary & pill counting) & dietary requirement

- Remind subject to complete and return at-home PedsQL, GI module & NMM (**Month 18 only**)

Should the subject report a new or worsening symptom, additional safety phone calls and/or safety visits may be scheduled at the investigator's discretion and safety labs performed. Any new or worsening abnormal lab should be followed and repeated until back to baseline or resolved.

Month 18 At-home Quality-of-Life surveys

- Complete and return Month 18 at-home PedsQL, GI module & NMM

Month 24 Treatment Visit

After 12 additional months of treatment, subjects will return to the site for Month 24 Treatment Visit.

- Record all medication use with start date and dose; check for prohibited medications.
- Inquire about AEs/Serious Adverse Events (SAEs) and IMP tolerability.
- Confirm compliance (subject diary & pill counting) & dietary requirement.
- Perform ECG, a physical exam with vital signs (blood pressure, heart rate, respiration rate, body temperature, weight).
- Obtain blood samples for clinical laboratory tests:
 - Complete Blood Count with differential: must include hemoglobin, hematocrit, platelet count, total white blood cell count with five-part differential count, and total red blood cell count.
 - Comprehensive Metabolic Panel: must include serum creatinine, blood urea nitrogen, glucose, total protein, albumin, total bilirubin, alanine aminotransferase, aspartate aminotransferase, alkaline phosphatase, electrolytes (sodium, potassium, chloride), calcium, bicarbonate, and creatine phosphokinase.
 - Coagulation Factors: prothrombin time reported as the international normalized ratio (INR) value (PT-INR), partial thromboplastin time (PTT or aPTT).
- Collect urine and blood samples for eicosanoid metabolites and other biomarkers.
- Month 24 CMR (\pm 7 day window)

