11.6 Randomization

Subjects will be randomly assigned to one of three treatment groups: low-dose ifetroban, high-dose ifetroban, placebo, using a 1:1:1 randomization ratio. All subjects will be treated with IMP daily for at a minimum of six months and a maximum of 12 months.

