11.8.6 Long-Term Safety and Efficacy Analyses

Subjects that complete the 12-month double-blind portion of the study will be eligible for an optional open label extension consisting of repeatable 12-month periods of treatment with high-dose ifetroban.

Safety will be monitored by continual adverse event reporting and changes in laboratory values as previously described.

For main efficacy endpoints (CMR parameters LVEF and myocardial strain), comparisons with respect to the change from Month 12 in LVEF and the change from Month 12 in myocardial strain at Months 24 and 36 will be performed for the ITT open label population using the Wilcoxon rank sum test. To assess treatment response the double-blind and open label studies, comparisons with respect to the change from baseline in LVEF and the change from baseline in myocardial strain at Months 24 and 36 will be performed for the ITT open label population using the Wilcoxon rank sum test. Subjects missing LVEF at either Month 12 or Month 24 will be excluded from this supportive analysis.

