#### **4.4.2 Treatments**

The following treatments will be given in the DB period:

- High Dose Ifetroban
- Low Dose Ifetroban
- Placebo

- Placebo group created from the Natural History dataset (see [Section 4.5](#))
- Overall

The following treatments will be given in the OL period:

- High Dose Ifetroban

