### **6.4.1 Efficacy Analyses in Open-Label Extension**

The following analyses will be performed for OL participants:

- One-year OL data (Month 12 to Month 24): Change from Month 12 in CMR parameters, PFT, QMT, and accelerometry will be summarized for all OL subjects, and by DB treatment assignment subgroups (High to High, Low to High, Placebo to High)
- Two-year total study data (Baseline to Month 24): Change from baseline in CMR parameters, PFT, QMT, and accelerometry will be summarized for continuous high-dose subjects compared to NHS matched subjects.
- Three-year total study data (for subjects completing 36 months): Change from baseline and from Month 36 in CMR parameters and PFT will be summarized

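### Four places in the long-term plan pool or mislabel extension subjects by ignoring year-1 treatment: the Protocol 6.5 label, the Protocol 11.8.6 change from baseline, the SAP three-year summary, and open-label safety

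*Protocol*

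**What the plan says.** **Design.** Protocol 11.6 allocates subjects to "low-dose ifetroban, high-dose ifetroban, placebo, using a 1:1:1 randomization ratio". Protocol 8.1.3 gives the entry rule: "Patients who complete 12 months of treatment are eligible to participate in a repeatable open-label extension period of 12 months". Protocol 7.1 fixes the extension treatment: "The open label study consisting of high-dose ifetroban treatment will be conducted in repeatable periods of 12 months".

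**Protocol, long-term efficacy.** Section 6.5 defines the endpoint as "Efficacy of ifetroban over 24 to 36 months of dosing (for the open label population", measured from baseline or from Month 12. Section 11.8.6 plans one set of comparisons from Month 12 and a second set from baseline: "comparisons with respect to the change from baseline in LVEF and the change from baseline in myocardial strain at Months 24 and 36". Both are run "at Months 24 and 36 will be performed for the ITT open label population using the Wilcoxon rank sum test". No split by year-1 arm is stated.

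**SAP, long-term efficacy.** Section 6.4.1 reports Month 12–24 for all entrants and for High to High, Low to High and Placebo to High. It limits baseline-to-Month 24 to continuous high dose against natural history, and 14.3.7 lays out the tables in the same way. Section 6.4.2 analyses durability by year-1 assignment and later treatment over the whole study. The three-year bullet carries no split: "Three-year total study data (for subjects completing 36 months): Change from baseline and from Month 36 in CMR parameters and PFT". Sections 4.4.4 and 8 declare no changes from the protocol's methods.

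**SAP, safety.** Section 4.4.2 introduces the open-label list with "The following treatments will be given in the OL period" and names one entry, high-dose ifetroban. Section 7 summarises safety by visit, treatment group, subgroup and overall. The subgroups in 6.5 are disease stage, ambulation and background therapy.

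**The concern.** The extension mixes three exposure histories. A change from baseline taken over all entrants and described by 24 to 36 months of dosing counts a placebo year as dosing. It then estimates neither the effect of continuous high dose nor that of the stated duration.

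The protocol and the SAP also define different populations for the baseline-to-Month 24 result while the SAP says nothing has changed. Two versions of the same result would then each have a claim to be the planned one.

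Safety is the trial's primary objective. At the Month 12 switch, placebo-first subjects meet ifetroban for the first time and low-dose-first subjects step up threefold (50 to 150 mg, or 100 to 300 mg). Events linked to those changes would sit in one column with subjects who have already completed a year of high dose.

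**Working it through.** **1. Months of ifetroban.** Inputs: a 12-month year 1 and high dose for all afterwards (Protocol 7.1, 8.1.3, 11.6).

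| Sequence | Any ifetroban at Month 24 / 36 | High dose at Month 24 / 36 |
|---|---|---|
| High to High | 24 / 36 | 24 / 36 |
| Low to High | 24 / 36 | 12 / 24 |
| Placebo to High | 12 / 24 | 12 / 24 |

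The Protocol 6.5 label of 24 to 36 months is reproduced for two of the three sequences. It is 12 months too long for Placebo to High.

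**2. Pooled exposure, assuming equal thirds.**
- Any ifetroban: (24 + 24 + 12)/3 = 20 of 24 months (83%); (36 + 36 + 24)/3 = 32 of 36 months (89%).
- High dose: (24 + 12 + 12)/3 = 16 of 24 months (67%); (36 + 24 + 24)/3 = 28 of 36 months (78%).

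**3. Share of the continuous high-dose effect kept by a pooled change from baseline.** Assume also that the effect against the untreated course accrues linearly, that low dose gives a fraction r of the high-dose effect, and that the study baseline is used for everyone. Working in years:
- Month 24: [2 + (1 + r) + 1]/3 ÷ 2 = (4 + r)/6, which is 67%, 75% and 83% for r = 0, 0.5 and 1.
- Month 36: [3 + (2 + r) + 2]/3 ÷ 3 = (7 + r)/9, which is 78%, 83% and 89%.

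**4. Change from Month 12.** Every entrant has 12 months of high dose at Month 24 and 24 months at Month 36 after that reference visit. Pooling causes no dilution by exposure time.

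**5. Baseline definitions side by side.** SAP 4.4.1 sets baseline for both periods at the last value on or before starting ifetroban. Taken literally, that is Month 12 for placebo-first subjects and pre-study for the others, so a pooled Month 24 change would mix 12-month and 24-month intervals. The shares in step 3 would then not apply. SAP 14.3.4 uses Month 12 for everyone in the open-label matching model.

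**6. Three-year reference visit.** SAP 6.4.1 asks for change from Month 36 in subjects completing 36 months. At Month 36 no later value exists to compare. Protocol 11.8.6 uses Month 12.

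**7. Safety.** SAP 7.1 defines a treatment-emergent event by onset or worsening after dosing, which for a placebo-first subject began with placebo. SAP 3.8 starts the open-label period at the first open-label dose, so the date is available, but the treatment-emergent definition does not use it. Protocol 11.2.1 ends the treatment-emergent period with the Treatment Period, which is Month 12 under Protocol 8.1. As an illustration with assumed rates, 30% in newly exposed placebo-first subjects and 10% in the other two thirds pool to (30 + 10 + 10)/3 = 16.7%; 20% and 5% pool to 10%.

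**The case against.** The strongest reply is that the SAP governs the detail, as Protocol section 11 says, and that it already separates the sequences. This stands for most SAP efficacy. A reader might infer that the extension is analysed throughout as one high-dose group, or that the split exists only for Month 12–24. The documents do not support either reading, given the High to High restriction to Month 24 and the durability analysis by sequence. The SAP's baseline-to-Month 24 tables contain only High to High and natural history, so the 67–83% figure does not describe them.

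Other points that stand:
- Protocol 11.8.6 names a population but not the two groups that a rank sum test needs. That the test sets one pooled arm against a comparator is therefore an inference. Protocol 11.5, which compares open-label high-dose subjects with natural history at Months 12, 24 and 36, makes it plausible.
- Low to High subjects do have 24 to 36 months of ifetroban; only their time on high dose is shorter.
- Placebo-first subjects are not the only ones with a new exposure, because Low to High subjects first meet high dose at Month 12.
- The primary endpoint covers baseline to 12 months and is untouched. Adverse events are also listed by subject, and Protocol 13.1 provides real-time unblinded safety review.
- The table shells are in a separate document and might show more columns.

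None of this corrects the Protocol 6.5 label, divides the protocol's population, adds a split at three years or gives extension safety a column by year-1 arm.

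**Conclusion.** The point holds for four places: the Protocol 6.5 label; the undivided population for change from baseline in Protocol 11.8.6, which conflicts with SAP 6.4.1 and 14.3.7; the SAP three-year summary; and open-label safety. It should be corrected, but it does not undermine the SAP's Month 24 efficacy analyses or anything measured from Month 12.

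The label error of 12 months for placebo-first subjects follows directly from the design. The shares of 67–83% (Month 24, protocol analysis only) and 78–89% (Month 36) are illustrations that rest on equal thirds, linear accrual, an assumed low-dose fraction and a common study baseline. A reader might take a third of entrants as placebo-first. That is only the expectation from 1:1:1 allocation, because entry is optional and limited to completers and the documents give no entrant counts. The size of any safety dilution cannot be derived from the documents.

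**What to change.** - **Protocol 6.5:** label the endpoint by study month, not by months of dosing.
- **Protocol 11.8.6:** align it with SAP 14.3.7 and name the groups compared.
- **Month 24 and Month 36 change from baseline:** present High to High, Low to High and Placebo to High separately. State the baseline for each sequence and reconcile SAP 4.4.1 with 14.3.4.
- **SAP 6.4.1, three-year bullet:** apply the same split and correct the reference visit.
- **SAP 4.4.2 and 7:** tabulate open-label adverse events, laboratory values and ECG by the same three sequences, with the pooled column last. Time them from the first ifetroban dose for placebo-first subjects and from the Month 12 switch for Low to High.
- **SAP 4.4.4 and 8:** record any difference from the protocol that remains.

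The cost is wording and table columns, with no new data. The downside is small groups: 48 completers over three arms gives at most about 16 per sequence, so these tables would be descriptive.
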